2.2 Schedule of Events

Table 2-1: Schedule of Events

	Screening /Baseline (7 to 45 Days) ^a			Dou	ble-blind	Treatmei	nt Period ((12 Weeks))		Follow-up (or Early Termination) (6 Weeks)
Study Day / Week	Day -45 to Day -1a	Day 1	Day 14 Week 2 ±3 days	Day 28 Week 4 ±3 days	Day 42 Week 6 ±3 days	1	Day 70 Week 10 ±3 days	Day 71 V7+24 hr	Day 77 V7+7 days ±3 days	Day 84 Week 12 ±3 days	Week 18 ±7 days
Clinic Visit (V)	V1 ^a	V2	V3	V4	V5	V6	V7	V8	V9	V10	V11
Informed Consent	X										
Inclusion/Exclusion Criteria	X	X									
Height and Weight (BMI)	X										
Demographics and Medical History	X										
Physical and Neurological Examination (C=complete; T=targeted)	С	Т	Т	Т	Т	Т	Т			С	С
12-lead Electrocardiogram (ECG)	X	Xb		X		X				X	X
Motor and Sensory Nerve Conduction Studies	X										X
Urine Drug Screen and Urine Pregnancy Test	X a									X	X
Total Neuropathy Score-Nurse (TNSn)	X	X	X	X	X	X	X			X	X
Strength and Deep Tendon Reflexesi	X	X	X	X	X	X	X			X	X
Urinalysis	X	X	X	X	X	X	X			X	X
Vital Signs ^c	X	X	X	X	X	X	X	X	X	X	X
CCI											
Randomisation		Xe									
Training and Reminders on Rating Pain and Entering Ratings on ePRO System ^d	X	X	X	X	X	X	X			X	
Study Drug Infusion (Dosing)		X	X	X	X	X	X				
Injection Site Assessment		X	X	X	X	X	X			X	X
Daily Pain Diary (NRS) via ePRO	X ^d	X	X	X	X	X	X	X	X	X	X
Daily Sleep Interference Scale (DSIS) via ePRO	X ^d	X	X	X	X	X	X	X	X	X	X
Galer Neuropathic Pain Scale	X			X		X				X	X
Patient Global Impression of Change (PGIC)				X		X				X	X
36-item Short-Form Health Survey (SF-36)	X									X	

	Screening /Baseline (7 to 45 Days) ^a			Dou	ble-blind	Treatmer	nt Period ((12 Weeks)			Follow-up (or Early Termination) (6 Weeks)
Study Day / Week	Day -45 to Day -1a	Day 1	Day 14 Week 2 ±3 days		Day 42 Week 6 ±3 days		Week 10	Day 71 V7+24 hr	Day 77 V7+7 days ±3 days	Day 84 Week 12 ±3 days	Week 18 ±7 days
Clinic Visit (V)	V1 ^a	V2	V3	V4	V5	V6	V7	V8	V9	V10	V11
Blood Collection for:											
Haematology, Chemistry, and Coagulation	X	X	X	X	X	X	X			X	X
Serology (HIV, hepatitis B and C, and tuberculosis)	X										
Pharmacogenetic Sampling (Optional)	X										
Haemoglobin A ₁ c	X										
Immunogenicity (ADA) Sampling	X		Xf	Xf		Xf	Xf			X	X
CCI											
Pharmacokinetic Sampling ^h		Xf	Xf	Xf	Xf	Xf	Xh	X^h	Xh	Xh	Xg
CCI											
Adverse Events	X	X	X	X	X	X	X	X	X	X	X
Rescue Medication Use ^d	X ^d	X	X	X	X	X	X	X	X	X	
Concomitant Medications and Therapies	X	X	X	X	X	X	X	X	X	X	X

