Peripheral neuropathy—both autonomic and sensory—has also been identified as a risk with anti-NGF antibodies (Bélanger et al. 2018; Dewanjee et al. 2018). 33,34 In the MEDI7352 13-week good laboratory practice toxicology study undertaken in rats, axonal degeneration has been observed in peripheral nerves. No clear dose-response relationship has been observed for this effect, although a trend for increased 'average' severity with increasing dose was noted. It is unclear whether sensory nerves or motor nerves or both are affected. No functional consequences have been observed in neurobehavioural assessments in the animals and the effect has been described as non-adverse in the rodents. The underlying mechanism and potential relevance of the finding to humans is unknown. It is not known whether MEDI7352 might worsen a pre-existing neuropathy as a function of NGF inhibition. For the present clinical study, the risk will be managed through appropriate peripheral nervous system monitoring and will include nerve conduction studies (NCS).

TNF-alpha inhibitors carry labelled safety warnings and precautions regarding the risk of serious infections (including tuberculosis [TB], bacterial sepsis, invasive fungal infections, and other opportunistic infections) and malignancies (including lymphoma and other malignancies). Additional warnings and precautions for etanercept include exacerbation or new onset of

demyelinating disease, lymphoma, pancytopenia or aplastic anaemia, new onset or worsening congestive heart failure, and reactivation of hepatitis B virus (HBV).

General risks of biologic therapies include infusion-related reactions (defined as a collection of signs and symptoms ranging from local skin reactions at the injection site, pyrexia, and an influenza-like syndrome, to an acute anaphylaxis, usually occurring within 2 hours of the infusion; hypersensitivity reactions; and development of anti-drug antibodies to MEDI7352. Antidrug antibodies to MEDI7352 could result in immune-complex disease (with manifestations including arthralgia, serum-sickness, and vasculitis), auto-immunity, or altered MEDI7352 levels or activity.

A summary of the pharmacological properties and known potential risks of MEDI7352 is provided in the current version of the IB. The investigator must become familiar with all sections of the MEDI7352 IB before the start of the study.

OBJECTIVES

Primary Objective

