- bilateral decrease or absent reflexes at the ankles, or bilateral decrease of a sensory sign in the distal lower extremities, based on medical history and peripheral neurological examination. [NOTE: for sensory evaluation, the relevant components of the TNSn for the lower limb should be undertaken, to include sensory symptom score, pin sensibility score, and vibration sensibility score.]
- 9. A mean pain intensity score of ≥4, as measured on an 11-point (0 to 10) NRS by completion of a subject diary for a minimum of 7 days prior to Day 1 (ie, Day -7 to Day -1). At least 5 of 7 days need to be recorded by the subject to obtain a valid baseline value. Pain scores from Day -7 to Day -1 will be centrally reviewed by the study team, and if there is significant variability in the scores during this baseline period of pain evaluation, it will be discussed with the investigator and the subject may be excluded.

Concomitant medication

- 10. The subject must be willing and able to discontinue all NSAID or COX-2 analgesic therapy from the start of the washout period until the end of follow-up. This includes over-the-counter (OTC) pain medications and topical analgesics that contain an NSAID or COX-2 inhibitor. The use of NSAIDs (eg, ibuprofen, naproxen) or COX-2 medications (eg, celecoxib) at any time during the study and through to completion of drug washout (5 half-lives) is prohibited and contraindicated.

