8.3 Premature Subject Withdrawal

All subjects will be advised that they are free to withdraw from participation in this study at any time, for any reason, and without prejudice. Subjects must be withdrawn from the study if they withdraw consent to participate. Investigators must attempt to contact subjects who fail to attend scheduled visits by telephone or other means to exclude the possibility of an AE being the cause of withdrawal. Should this be the cause, the AE must be documented, reported, and followed as described in Section 11.2.

The sponsor reserves the right to request the withdrawal of a subject due to protocol deviations or other reasons.

The investigator also has the right to withdraw subjects from the study at any time for lack of therapeutic effect that is intolerable or otherwise unacceptable to the subject, for intolerable or unacceptable AEs, intercurrent illness, noncompliance with study procedures, administrative reasons, or in the investigator's opinion, to protect the subject's best interest.

If a subject is withdrawn before completing the study, the reason for withdrawal and the date of discontinuation will be recorded on the appropriate page of the case report form (CRF) or electronic case report form (eCRF). Whenever possible and reasonable, the evaluations that were to be conducted at the completion of the study should be performed at the time of premature discontinuation.

A participant will be considered lost to follow-up if he or she fails to return for scheduled visits and is unable to be contacted by the study site staff.

The following actions must be taken if a participant fails to return to the clinic for a required study visit:

- The site will attempt to contact the participant and reschedule the missed visit and counsel the participant on the importance of maintaining the assigned visit schedule and ascertain if the participant wishes to and/or should continue in the study.
- Before a participant is deemed lost to follow-up, the investigator or designee will make every effort to regain contact with the participant (where possible, 3 telephone calls and, if necessary, a certified letter to the participant's last known mailing address or local equivalent methods). These contact attempts should be documented in the participant's medical record or study file.

• Should the participant continue to be unreachable, he or she will be considered to have withdrawn from the study with a primary reason of lost to follow-up.

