9.1.1 Dose, Route of Administration, and Dosing Schedule

Once randomized, subjects will be dosed with either MEDI7352 or placebo on Day 1, Day 14, Day 28, Day 42, Day 56, and Day 70. MEDI7352 or placebo will be administered IV over a 60-minute period.

MEDI7352 or placebo should be administered by the investigator or site personnel prepared to manage infusion reactions and anaphylaxis. The infusion rate may be slowed or interrupted if the subject develops an infusion reaction. [NOTE: If the infusion is slowed or interrupted, the total infusion time should not exceed 4 hours at room temperature.] Investigators/site personnel should be aware of the risk of hypersensitivity reactions, which may present as infusion reactions, and monitor subjects closely. In the event of a serious reaction, MEDI7352 or placebo administration must be discontinued immediately and the appropriate medical therapy administered.

Subjects will be dosed as outpatients but should remain under clinical supervision and should be monitored for no less than 4 hours after completion of each infusion. Should clinical features of acute hypersensitivity occur, an extended period of monitoring in an appropriate environment may be relevant, based on clinical judgement. This may include, but is not necessarily limited to, monitoring vital signs and observing for any untoward reactions. Consultation with the appropriate local clinical services may be warranted (eg, high dependency or intensive therapy unit).

Subjects should be made aware of the potential risks of acute hypersensitivity and infusion-related reactions, the signs and symptoms of such reactions, and the importance of immediately seeking medical attention should they occur.

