10.2.3 Follow-up (or Early Termination) Evaluation (Week 18)

At 6 weeks after the last visit (8 weeks after the last administration of the IP) or upon early termination of the study, the following procedures will be performed:

- 1. Perform Galer NPS.
- 2. Perform PGIC.
- 3. Perform a complete physical and neurological examination (excluding the genitourinary examination, unless warranted).
- 4. Perform TNSn, strength (dorsiflexion), and deep tendon reflex (knee and ankle) assessments.
- 5. Perform 3 replicates of 12-lead ECGs (with printouts) after the subject has been resting in the supine position for at least 10 minutes.
- 6. Perform motor and sensory NCS.
- 7. Collect blood samples for the following:
 - chemistry, haematology, and coagulation

AD-MW-07.06 08-Dec-2017 733 of 938 Page 60 of 114

- immunogenicity (ADA) testing
- PK and CCI (only if this is an Early Termination Visit)
- 8. Collect urine sample for the following:
 - urinalysis
 - urine pregnancy test (for women who are not surgically sterile)

- 9. Measure sitting vital signs (HR, BP [sitting after a 5-minute rest], respiratory rate, and temperature). To assess orthostasis, repeat the measurement of BP and pulse 1 (>1 minute, <3 minutes) minute after the subject stands.
- 10. Assess the IV injection site for local reactions.
- 11. Record AEs and concomitant medications and therapies.

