11.2 Event Assessment and Follow-up of Adverse Events

The occurrence of an AE or SAE may come to the attention of study personnel during study visits and interviews of a study participant presenting for medical care, or upon review by a study monitor.

All AEs including local and systemic reactions not meeting the criteria for SAEs will be captured on the appropriate eCRF. Information to be collected includes event description, time of onset, clinician's assessment of severity, relationship to study product (assessed only by those with the training and authority to make a diagnosis), and time of resolution/stabilization of the event. All AEs occurring while on study must be documented appropriately regardless of relationship. All AEs will be followed to adequate resolution.

Any medical condition that is present at the time that the participant is screened will be considered as baseline and not reported as an AE. However, if the study participant's condition deteriorates at any time during the study, it will be recorded as an AE.

Changes in the severity of an AE will be documented to allow an assessment of the duration of the event at each level of severity to be performed. AEs characterized as intermittent require documentation of onset and duration of each episode.

The site staff will record all reportable events with start dates occurring any time after informed consent is obtained until 7 (for nonserious AEs) or 30 days (for SAEs) after the last day of study participation. At each study visit, the investigator will inquire about the occurrence of AE/SAEs since the last visit. Events will be followed for outcome information until resolution or stabilization.

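### The Week 18 follow-up and the early termination evaluation are one visit, so subjects withdrawn early have no scheduled examination 8 weeks after the last dose, and TEAE windows are unequal

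*Protocol*

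**What the plan says.** - **One visit for two purposes.** Section 10.2.3 places the evaluation "At 6 weeks after the last visit (8 weeks after the last administration of the IP) or upon early termination of the study". Table 2-1 has one column for both (V11, Week 18 ±7 days), and Section 10.2 counts a single follow-up visit.
- **Withdrawn subjects.** Section 8.3 says that, where possible, "the evaluations that were to be conducted at the completion of the study should be performed at the time of premature discontinuation". Adverse events the subject cannot accept are among the grounds on which the investigator may withdraw a subject. No section schedules a visit after that.
- **Subjects whose IP is stopped for safety.** Section 9.3.1 ends further infusions. It does not say whether the subject leaves the study or stays to Week 18.
- **AE collection.** Section 11.2 records events "until 7 (for nonserious AEs) or 30 days (for SAEs) after the last day of study participation". Section 11.2.5 follows reported AEs until resolved, stable or explained. Section 11.2.6.2 keeps suspected serious ADRs reportable without a time limit.
- **TEAE window.** Section 11.1.6 closes it 30 days after the last IP administration. Section 13.1.6.1 closes it at the Follow-up or the Early Termination Visit, whichever is earlier.
- **Nerve conduction.** Section 10.3.3.1.9 and Table 2-1 place NCS at baseline and at the follow-up (or early termination) visit only. Section 13.1.6.6 lists the results and leaves a summary optional.

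**The concern.** Section 5.3 names neuropathy, joint events, infection and immunological reactions as potential risks, says it is unknown whether the drug could worsen an existing neuropathy, and relies on monitoring to manage that risk. Every subject has neuropathy at entry, and Section 12 provides no data safety monitoring board, so the scheduled examinations carry much of the safety evidence. A subject withdrawn for an adverse event has the final examination moved to the day of exit, and nobody is scheduled to look again at 8 weeks.

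The analysis inherits this. Under Section 13.1.6.1 the time at risk after the last dose depends on whether the subject completed. If withdrawal differs between arms, crude TEAE percentages are not like for like. The SAP cannot recover an examination that was never done or an event that was never collected.

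**Working it through.** **Inputs.** Last infusion on Day 70, the final entry in "Day 1, Day 14, Day 28, Day 42, Day 56, and Day 70" (Section 9.1.1). End-of-treatment visit on Day 84 (Section 10.2.2). Follow-up at Week 18 ±7 days (Table 2-1). AE collection of 7 days (non-serious) and 30 days (serious) after participation ends (Section 11.2). Anticipated withdrawal about 10% (Synopsis, sample size). Total randomised 272 (Section 7.1).

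**Step 1: reproduce the plan's figure.** Week 18 = 18 × 7 = Day 126. 126 − 70 = 56 days = 8 weeks after the last dose, and 126 − 84 = 42 days = 6 weeks after the previous visit. Both match Section 10.2.3. With the ±7-day window the visit falls 49 to 63 days after the last dose.

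**Step 2: post-dose observation by group.** The protocol does not say when early terminators leave. We assume an exit within one 14-day dosing interval of the last infusion.

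| Days after last dose | Completers | Early terminators (assumed exit at day 0 to 14) |
|---|---|---|
| Last scheduled examination | 56 | 0 to 14 |
| Non-serious AE collection ends | 56 + 7 = 63 | 0 + 7 = 7 to 14 + 7 = 21 |
| SAE collection ends | 56 + 30 = 86 | 0 + 30 = 30 to 14 + 30 = 44 |

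The gap in scheduled observation is 56 − 14 = 42 to 56 − 0 = 56 days. If the 3-day visit window is added (exit at day 17), collection ends at day 24 and day 47, which changes nothing of substance.

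**Step 3: the two TEAE definitions.** Under Section 13.1.6.1 completers contribute about 56 days after the last dose and early terminators about 0 to 14. Under Section 11.1.6 the limit is 30 days for everyone, but non-serious AE collection for these early terminators stops at day 7 to 21. Choosing the 30-day definition alone would therefore not equalise the groups. The later visit is needed as well.

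**Step 4: number affected.** 0.10 × 272 = 27.2, so about 27. If withdrawal were 5% or 20% (an assumed range), the figures would be about 14 and 54. Each is a ceiling at its rate, because the withdrawal rate is overall and not broken down. It can include subjects who withdraw consent or are lost to follow-up, for whom no later visit can be had. It can include exits after Day 84, which already have 14 to nearly 56 days after a Day 70 dose. Section 10.2.2.1 also classes subjects randomised but never dosed as early terminated, and they have no post-dose period.

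**The case against.** The other side is right on several points.

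- **Stopping IP is not leaving the study.** A reader might infer that everyone stopped for safety loses the 8-week follow-up. Section 9.3.1 does not say so. The loss is stated only for subjects withdrawn from the study. For the others the fault is silence.
- **Follow-up does not vanish.** A reader might infer that late harm goes unseen. SAEs are collected for 30 days after exit, reported AEs are followed up, suspected serious ADRs stay reportable, and Appendix A sets its own follow-up for potential Hy's Law cases. These provisions cover known or spontaneously reported events. They do not replace an examination with laboratory tests at 8 weeks.
- **Nerve conduction.** A reader might infer a biased treatment comparison. None is planned: the results are listed and perhaps summarised. TNSn, strength and reflexes are also scored at every dosing visit and at Week 12. What remains is that NCS values at different times since the last dose are hard to read together.
- **Dose-related stopping.** Nothing in the available text shows that withdrawal rises with dose, so it cannot be said that harm is under-recorded most in the higher-dose arms. Unequal windows are a weakness whichever way withdrawal falls.
- **NSAID ban.** Section 8.2.1 says NSAID use "through to completion of drug washout (5 half-lives) is prohibited and contraindicated". The available text gives no half-life, so it cannot be judged whether even Week 18 covers that period. The point is not pressed.
- **Moving measurements.** Shifting NCS and the final ADA sample from exit to 8 weeks could lose the only post-baseline value in a subject who does not come back. They should stay at exit.

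**Conclusion.** The point stands in limited form. Followed exactly, the protocol gives a subject withdrawn early no scheduled examination 8 weeks after the last dose, and it does not say what happens to subjects whose IP alone is stopped under Section 9.3.1. The shortfall is about 42 to 56 days of scheduled observation if exit falls within one dosing interval, and less for later exits. What is lost is the 8-week examination and late non-serious AEs, for at most about 27 of 272 subjects at the anticipated withdrawal rate. Separately, Sections 11.1.6 and 13.1.6.1 contradict each other on the TEAE window, and the second makes the window depend on whether the subject completed. The primary efficacy analysis is untouched. The case for change is that safety capture and comparability improve at little cost.

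**What to change.** 1. In Sections 8.3 and 10.2.3 and Table 2-1, list the early termination evaluation and the follow-up visit separately.
2. Keep the early termination evaluation at exit with its full content, including NCS and ADA.
3. Ask every dosed subject who has not withdrawn consent to attend the existing follow-up visit 8 weeks after the last infusion for AEs, neurological examination, TNSn, strength, reflexes and laboratory tests. Count that visit as the last day of participation for AE and SAE collection.
4. State whether subjects stopped under Section 9.3.1 remain on the visit schedule.
5. Reconcile Sections 11.1.6 and 13.1.6.1 to one fixed post-dose TEAE window for all subjects.
6. Show time since last dose in the NCS listings.

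The cost is one amendment and, at the anticipated withdrawal rate, at most about 27 extra attendances at a visit that already exists. Some subjects will not return, but with the exit evaluation kept whole they are no worse documented than under the present plan.

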10.2.2.5 Day 84 (End-of-treatment; Week 12)

The following procedures will be performed at the end-of-treatment visit on Day 84 (2 weeks after the last dose):

- 1. Perform Galer NPS.
- 2. Perform PGIC.
- 3. Perform SF-36.
- 4. Perform a complete physical and neurological examination (excluding the genitourinary examination, unless warranted).

- 5. Perform TNSn, strength (dorsiflexion), and deep tendon reflex (knee and ankle) assessments.
- 6. Perform 3 replicates of 12-lead ECGs (with printouts) after the subject has been resting in the supine position for at least 10 minutes.
- 7. Measure sitting vital signs (HR, BP [sitting after a 5-minute rest], respiratory rate, and temperature). To assess orthostasis, repeat the measurement of blood pressure and pulse 1 minute (>1 minute, <3 minutes) after the subject stands.
- 8. Collect blood samples for the following:
 - chemistry, haematology, and coagulation
 - immunogenicity (ADA) testing
 - PK
 - CCI
- 9. Collect urine sample for the following:
 - urinalysis
 - urine pregnancy test (for women who are not surgically sterile)

CCI

- 10. Assess the IV injection site for local reactions.
- 11. Record AEs and concomitant/rescue medications and therapies.
- 12. Remind the subject to continue entering their daily pain and DSIS into the ePRO system and rescue medication into the paper diary.
- 13. Schedule the subject to return to the clinic for the Week 18 visit.

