13.1.4 Efficacy Analysis

All efficacy variables will be summarized descriptively including number of observations, mean, SD, minimum, median, and maximum for continuous variables, and frequency of observations in each category and percentage for categorical variables.

Primary and secondary endpoint efficacy data will be tabulated according to the 'Observed Cases' approach. In addition, if there is missing data at a key analysis time-point (Weeks 4, 8, and 12) then results will also be tabulated according to 'Last-Observation-Carried-Forward' (LOCF) and 'Baseline-Observation-Carried-Forward' (BOCF). For example, if an endpoint is missing from a post-randomisation visit then the last non-missing post-baseline endpoint recorded prior to the visit will replace the missing value. For endpoints with separate scales, if an individual scale item is missing then the item will be carried forward from the previous visits rather than the total score. For post-baseline diary data, if a subject has at least 4 out of 7 days' diary data prior to the visit, then this will be taken as a valid observed weekly average score. However, if a subject has 3 or fewer days of diary data, this will be counted as a missing weekly score, and the LOCF approach will carry forward the last 7 non-missing entries of the diary data prior to the visit in order to calculate the weekly mean score at endpoint score.

The main statistical analysis of the primary efficacy endpoint at Week 12 will use the multiple comparison procedure modelling (MCP-Mod) approach on LOCF data, which is a well-established statistical methodology for establishing both the existence of a dose response and modelling the underlying dose-response relationship. Both EMA (2014)⁴⁴ and FDA (2015)⁴⁵ have recognized MCP-Mod as an efficient statistical methodology for model-based design and analysis of Phase 2 dose finding studies under model uncertainty.

There are two steps to MCP-Mod:

13-Apr-2022

- 1. The 'MCP' step is a rigorous method to establish presence of a dose response while protecting the type I error and, if the dose-response relationship is statistically significant, then
- 2. The 'MOD' step estimates the dose response function and associated model parameters, such as ED50 (the effective dose for 50% of the population) in the case of E_{max} relationship.

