13.1.4.1 Efficacy Endpoints

13-Apr-2022

The primary efficacy endpoint is the change in the weekly average of the average daily pain scores from the baseline week to Week 12, as measured on an 11-point (0-10) NRS.

The secondary endpoints are the following:

- Change in the weekly average of the average daily pain score, as measured on an 11-point (0-10) NRS, from baseline to Weeks 2, 4, 6, 8, and 10 of treatment and the week before the follow-up visit.
- Percentage of subjects who have achieved ≥30% and ≥50% reductions in the weekly average of the average daily pain score from baseline during Weeks 4, 8, and 12 of treatment and the week before follow-up.
- Change in Galer NPS from baseline to Days 28, 56, and 84 of treatment and the follow-up visit.
- Change in DSIS from baseline to Days 28, 56, and 84 of treatment and the follow-up visit.

- Proportion of subjects who have 'improved', 'much improved', or 'very much improved' relative to baseline on the PGIC on Days 28, 56, and 84 of treatment and the follow-up visit.
- Change in the SF-36 from baseline to Day 84 of treatment.
- Usage of rescue medication (yes/no) from baseline to Week 12 of treatment.

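### The early-termination visit has no SF-36 and does not name rescue use, so subjects who leave before Day 84 have no scheduled post-baseline SF-36

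*Protocol*

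**What the plan says.** Section 10.2.3 sets out a single list of procedures for both visits, introduced by the words "8 weeks after the last administration of the IP) or upon early termination of the study, the following procedures will be performed". Table 2-1 matches it with one shared column for follow-up and early termination. The list includes the Galer neuropathic pain scale (NPS) and the global impression of change (PGIC) but not the SF-36. One blood-sampling item, PK, is marked as applying only when the visit is an early termination.

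The SF-36 appears in the screening list (10.2.1.1) and the Day 84 list (10.2.2.5), and Table 2-1 marks only those two visits. The secondary endpoint in 13.1.4.1 is "Change in the SF-36 from baseline to Day 84 of treatment".

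For medication, the lists for Days 14 to 70, 71, 77 and 84 say "Record AEs and concomitant/rescue medications and therapies". The Week 18/early-termination list says "Record AEs and concomitant medications and therapies". The rescue row of Table 2-1 is marked from screening to Day 84 and is blank in the last column.

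Section 13.1.4 tabulates secondary endpoints as observed cases and, if data are missing at Weeks 4, 8 or 12, also by last observation carried forward (LOCF) and baseline observation carried forward (BOCF). Under LOCF, "the last non-missing post-baseline endpoint recorded prior to the visit will replace the missing value". Section 8.3 says that, where possible and reasonable, "the evaluations that were to be conducted at the completion of the study should be performed at the time of premature discontinuation".

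**The concern.** An early-termination visit exists largely to secure outcome data from people who will not reach the planned endpoint visit. Here it secures NPS and PGIC but not the SF-36. This cannot be left to the SAP: an analysis plan can choose how to handle a missing questionnaire, but it cannot recover one that was never given.

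At stake is one secondary endpoint. Its main comparison would rest on subjects who stayed to Day 84, and the LOCF table meant to bring in the others would add nothing. If leavers differ from stayers in health status, the collected data cannot show by how much. Section 14.6.2 widens the exposure: if the study is stopped early, sites may be asked to perform the early-termination assessments on everyone then taking part, again without an SF-36.

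The rescue point is smaller. The source is a paper diary kept by the subject (10.3.1.6), and the visit at which a leaver would hand it over carries no instruction to collect it.

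**Working it through.** The plan states no figure on this point, so the check is a comparison of its own sections followed by a simple count.

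**1. What is collected at each visit (Table 2-1 and Section 10.2)**

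| Item | Screening | Days 14 to 70 | Day 84 | Week 18 / early termination |
|---|---|---|---|---|
| SF-36 | yes | no | yes | no |
| NPS | yes | Days 28, 56 | yes | yes |
| PGIC | no | Days 28, 56 | yes | yes |
| Rescue row marked in Table 2-1 | yes | yes | yes | no |
| Rescue named in the visit's medication item | not compared (a screening item is blacked out) | yes | yes | no |

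A subject leaving before Day 84 passes through screening, some treatment visits and the early-termination visit. None of these after screening includes an SF-36.

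**2. What each planned analysis does with that subject's SF-36**

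- Observed cases (tabulation and repeated-measures model): no Day 84 value, so the subject does not contribute. With a single post-baseline time point, the model has no earlier outcome on which to base the missing one.
- LOCF: needs an earlier post-baseline value, and none is scheduled. The item-level rule for multi-scale endpoints has no earlier post-baseline visit either. The table can be produced but in effect repeats the observed cases.
- BOCF: carries the screening value forward, so the change is zero. This is the only planned approach that includes the subject.

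**3. Does Section 8.3 close the gap?**

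It turns on what completing the study means. Section 7.6 and Section 14.6.1 tie the completion or end of the study to the last visit of the last subject. Those are trial-level definitions, but the natural subject-level reading is the last visit, Week 18, where no SF-36 is done. If end of treatment was meant, Section 8.3 does call for an SF-36 and then disagrees with Section 10.2.3 and Table 2-1. Either way the text needs correcting.

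**4. How many subjects**

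- Randomised, all stages (Section 7.1): 10 + 30 + 67 + 165 = 272.
- Randomised, stages 2 to 4: 30 + 67 + 165 = 262.
- Withdrawal rate (synopsis, sample size): about 10%.
- All stages: 0.10 × 272 = 27.2, about 27.
- Stages 2 to 4: 0.10 × 262 = 26.2, about 26.

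These are upper bounds at that rate. The 10% is overall withdrawal, and anyone leaving between Day 84 and Week 18 already has a Day 84 SF-36. If the rate were 5% to 20% (assumed here, not in the protocol), the bound for stages 2 to 4 would run from 0.05 × 262 = 13 to 0.20 × 262 = 52.

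The 10% should not be applied to the 236 evaluable subjects: 0.90 × 262 = 235.8, so that number already appears to be net of 10%.

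**The case against.** **Rescue data.** A reader might infer that a leaver's last interval of rescue use is lost and that a user could be coded as a non-user. The documents do not support this. Sections 9.1.3 and 9.7.1 require all rescue use to be captured in the CRF, whatever the visit. Section 10.3.1.6 has subjects record it in the diary. Section 9.7 requires all concomitant medication, including over-the-counter products, to be recorded, and the early-termination list records concomitant medication. The rescue row of Table 2-1 also carries a footnote whose text is blacked out. What stands is a mismatch: capture is required, but the visit list and table do not name it.

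**Follow-up endpoints.** A reader might infer that early-termination NPS and PGIC values will be pooled with completers' follow-up values some 8 weeks after the last dose. Nothing says so. A shared procedure list is not a shared analysis window; Section 13.1.6.1 names the two visits separately, and assigning visits to time points is ordinary SAP content.

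**SF-36.** BOCF does include early leavers, so it is not true that every planned analysis is restricted to completers. Section 8.3 can also be read as calling for end-of-treatment evaluations. Both points soften the finding. Neither removes it: BOCF supplies an assumed zero change rather than an observation, and Section 8.3 is ambiguous and qualified by what is possible and reasonable.

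**Importance.** The primary endpoint comes from the daily electronic pain diary and is untouched. This concerns one secondary endpoint in a Phase 2 study. That is fair, and it sets the weight of the point.

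**Conclusion.** The point holds for the SF-36. As scheduled, subjects who withdraw before Day 84 have no post-baseline SF-36: at most about 26 of 262 in stages 2 to 4, or 27 of 272 overall, assuming the protocol's 10% withdrawal rate and its planned stage sizes. LOCF adds nothing for them, the observed-case analysis omits them, and only BOCF includes them. Section 8.3 does not clearly repair this.

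For rescue medication the defect is one of wording: its capture is required elsewhere but not named at this visit, unlike at every treatment visit after Day 1.

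No bias in SF-36 points can be attached to the gap. The protocol gives neither the difference between leavers and stayers nor withdrawal by arm, so any such figure would rest entirely on assumed inputs. This is an inexpensive improvement that secures otherwise unrecoverable secondary data, not a threat to the trial's main conclusion.

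**What to change.** In Section 10.2.3 and Table 2-1, add two items that apply only at early termination, in the way PK sampling is already handled there:

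- SF-36, if the subject has not reached Day 84;
- collection and review of the rescue-medication diary.

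Reword Section 8.3 to state which visit's evaluations are meant at premature discontinuation, so that it agrees with Section 10.2.3 and Table 2-1.

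The cost is one questionnaire and one diary check at a visit that already takes place, plus the amendment text and the matching eCRF entries.
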